### **Location of study**

The studies will be conducted in the Department of Surgery at Prince of Wales Hospital, Shatin, Hong Kong.

**Figure 1: The design of the integrated Fecobionics device and system.**

**Figure 2: Schematic representation of novel advanced analysis of pressure signals**

**Figure 3: Pressure signatures of healthy subject (AB), FI patient (CD) and CC patient (EF) during defecation of the device**

**Figure 4: LARS Questionnaire**

Do you ever have occasions when you cannot control your flatus (wind)?

	No, never	0
	Yes, less than once per week	4
	Yes, at least once per week	7

Do you ever have any accidental leakage of liquid stool?

	No, never	0
	Yes, less than once per week	3
	Yes, at least once per week	3

How often do you open your bowels?

	More than 7 times per day (24 hours)	4
	4–7 times per day (24 hours)	2
	1–3 times per day (24 hours)	0
	4–7 times per day (24 hours)	5

Do you ever have to open your bowels again within one hour of the last bowel opening?

	No, never	0
	Yes, less than once per week	9
	Yes, at least once per week	11

Do you ever have such a strong urge to open your bowels that you have to rush to the toilet?

	No, never	0
	Yes, less than once per week	11
	Yes, at least once per week	16

Total Score:

Interpretation:

0–20: No LARS

21–29: Minor LARS

30–42: Major LARS

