### Specific Aim 1: Anorectal pathophysiology of LARS patients

Objective: use fecobionics to obtain physiological and pathophysiological signatures of anorectal function in a heterogeneous group of LARS patients. Based on the epidemiology and symptomatology of LARS, it is expected that the heterogeneous group will contain an almost equal number of LARS patients with incontinence, frequency and urgency, and those primarily with constipation and feelings of incomplete emptying. Due to the spread (heterogeneity) in the patient group regarding symptoms, regression analysis will be the primary statistical tool to associate symptoms with experimental findings. We will also compare to age- and sex-matched healthy controls from already conducted studies.

Milestone: Describe the mechanosensory signature, variation of the measured variables, and computed endpoints in LARS patients.

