### Data collection:

Patients will be assessed at baseline and following will be recorded for all patients:

- Demographic data
- Body Mass Index (BMI)
- Significant Past Medical and Surgical History
- Obstetric History (female patients only)
- Rectal Cancer stage: TNM staging, location of tumour from anal verge on preop image

- Rectal Cancer treatment
  - o Neoadjuvant chemoradiotherapy/radiotherapy/chemotherapy
  - o Surgery – Open/Laparoscopic/Robotic/TaTME, level of anastomosis
  - o Post-operative complications
  - o Postop chemotherapy / radiotherapy
  - o Timing of defunctioning stoma (ileostomy / colostomy) closure
- LARS questionnaires: to assess Quality of life associated with LARS (Figure 4)

All patients will undergo the following tests:

- Integrated Fecobionics anorectal test (see clinical workflow below)
- High Resolution Anorectal Manometry (ARM) to assess resting and squeeze pressures, sensitivity, rectal capacity and recto-anal inhibitory reflex.
- Conventional balloon expulsion test
- Defaecography

Clinical data will be recorded and stored electronically in the hospital server. Completed questionnaires will be recorded and entered into database software and stored in the hospital server.

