### **Study design related to specific *Aim 1*: Anorectal pathophysiology of LARS patients**

Studies are planned to include a heterogeneous group of LARS patients with a broad scale of symptoms. We will study 30 patients recruited from a pool of postoperative patients who are under the care of our Department. The department has a large cohort of patients with LARS and it is anticipated that it will be easy to recruit the patients.

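### In Figure 4 the bowel-frequency item prints 4–7 a day twice, scored 2 and 5, and has no row below once a day; check the source page and clinic form and correct the label of the 5-point row

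*Combined protocol and SAP*

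**What the plan says.** Under Data collection, the protocol lists "LARS questionnaires: to assess Quality of life associated with LARS" among the items recorded at baseline for all patients. It points to Figure 4 and cites the development and validation papers for the score.

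In Figure 4, the item "How often do you open your bowels" has four rows, in this order:

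| Row | Label as printed | Score |
|---|---|---|
| 1 | above seven a day | 4 |
| 2 | "4–7 times per day (24 hours" | 2 |
| 3 | "1–3 times per day (24 hours" | 0 |
| 4 | "4–7 times per day (24 hours" (again) | 5 |

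The total is read as no LARS (0–20), minor LARS (21–29) or major LARS, the last printed as "30–42: Major LARS". No other section gives a different version of the item.

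Specific Aim 1 states that "regression analysis will be the primary statistical tool to associate symptoms with experimental findings". It expects an "almost equal number of LARS patients with incontinence, frequency and urgency, and those primarily with constipation and feelings of incomplete emptying". The study design section sets the size: "We will study 30 patients recruited from a pool of postoperative patients".

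**The concern.** One answer carries two scores, and one part of the frequency range has no answer. A patient at 4–7 a day can tick either of two identical rows. A patient below once a day must leave the item blank or choose a row that does not apply, and the documents give no rule for scoring a blank item.

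This is the only symptom questionnaire named in the data collection list, and Aim 1 includes patients whose main complaint is constipation, for whom a less-than-daily row is likely to matter. If the form is used as printed, the recorded symptom score can be wrong in either direction, and the analyst could not tell from the total which patients are affected.

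**Working it through.** **Inputs, all from Figure 4.** Possible scores by item: flatus 0, 4, 7; liquid leakage 0, 3, 3; bowel frequency 4, 2, 0, 5; repeat opening within an hour 0, 9, 11; urgency 0, 11, 16. Cut-offs fall between 20 and 21 and between 29 and 30. The printed maximum is 42.

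**Step 1: reproduce the printed maximum.** The maximum total is the sum of the item maxima.

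- With the 5-point row: 7 + 3 + 5 + 11 + 16 = 42, as printed.
- Without it, the highest frequency score is 4: 7 + 3 + 4 + 11 + 16 = 41, which does not match.

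So the 5 points belong on the scale, and deleting the row would be the wrong repair.

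**Step 2: which label is wrong.** The sum alone does not say which of the two identical labels is misplaced. The order of the rows does: rows 1 to 3 run downwards from above seven, to 4–7, to 1–3 a day, and a return to 4–7 in row 4 breaks the sequence. Rows 1 to 3 already cover once a day and above, so the only range left for row 4 is less than once a day. This is an inference; the exact wording has to come from the cited instrument.

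**Step 3: size of each error, taking row 4 as less than daily.**

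- A 4–7 a day patient who ticks row 4: recorded 5, correct 2, error 5 − 2 = +3.
- A less-than-daily patient who ticks row 3: recorded 0, correct 5, error 0 − 5 = −5.

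**Step 4: can these errors change the category?**

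- At 29/30, take no flatus problem (0), no leakage (0), repeat opening at least weekly (11) and urgency at least weekly (16), so the other four items sum to 27. At 4–7 a day the correct total is 27 + 2 = 29 (minor) and the recorded total 27 + 5 = 32 (major). At less than daily the correct total is 27 + 5 = 32 (major) and the recorded total 27 + 0 = 27 (minor).
- At 20/21, take urgency at least weekly (16) and zero on the other three items. At 4–7 a day the correct total is 16 + 2 = 18 (no LARS) and the recorded total 16 + 5 = 21 (minor). At less than daily the correct total is 16 + 5 = 21 (minor) and the recorded total 16 + 0 = 16 (no LARS).

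Both errors can therefore cross both cut-offs. These are worked examples; they do not say how often it would happen.

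**The case against.** The strongest reply is that this may not be an error in the plan at all. The text was extracted from a PDF by software, and the faulty label repeats word for word a label two rows above it, while the weights and bands otherwise agree. An extraction slip would look the same, and the documents cannot separate the two. The intended instrument can be identified from the cited papers. The Background also reports major LARS rates from the unit's own cohort followed since January 2016, which suggests, without proving it, that a working form already existed. All of this stands, and it is why the first step is a check rather than a correction of data.

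It is also fair to say that no specified analysis is shown to depend on the item. The protocol describes the questionnaire as a quality-of-life measure, its named endpoints are device measurements, eligibility has no score threshold, and no analysis by LARS category is planned. This stands too.

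A reader might go further and infer that the two errors bias the Aim 1 regression, falling differently on the incontinence and constipation groups, or that a sizeable share of the 30 patients would be misclassified. The documents do not support either. The LARS total is never named as the symptom variable, the number of patients who would tick the wrong row is unknown, and no comparison of the two groups' mean scores is specified. Counting the answer patterns that change category would not help, because patterns are not patients.

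What the reply does not remove is that the protocol directs staff to Figure 4 and, as it reads, the item there cannot be scored unambiguously.

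**Conclusion.** The point holds in a limited form and should be fixed. As printed, Figure 4 gives 4–7 a day two scores and leaves less than once a day without a row. The score of 5 is supported by the printed maximum of 42; its label is what is wrong. If the form is used as printed, the error for an affected patient is +3 or −5 points, enough to change the LARS category in some cases.

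This rests on three assumptions: that the source page carries the same label as the extracted text, that the page is the form patients complete, and that row 4 is meant for less-than-daily opening. The first two cannot be settled from the documents, and the third is an inference from the row order and the gap in coverage. An effect on the study's results is possible but not shown.

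**What to change.** Check the source page of Figure 4 and the form in clinic use against the validated instrument cited under Data collection. Correct the label of the 5-point row, taking the wording from that instrument, before the form is used. Keep all four scores, so that the maximum stays at 42. If the clinic form is already right, only the figure needs changing; if the source page is right as well, nothing does.

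If the faulty form has already been given to patients, confirm bowel frequency with those who ticked the lower 4–7 row, left the item blank or ticked 1–3 a day, and re-score them. Ticks on the upper 4–7 row and on the top row already carry the intended score. The confirmation has to come from the patients, because the baseline data list names no other source of bowel frequency.

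The cost is one label and a check of one form. If re-scoring is needed, the small downside is reliance on patients' recall of their bowel frequency at the time of testing.
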